Given the well-documented inflammatory and oxidative stress burden in ESRD and its implication to cardiovascular (CVD) mortality ¹⁹, current research focuses on anti-inflammatory nutritional and pharmacological strategies ²⁰⁻²³. Although results from these trials hold promise, different sources of inflammation such as untreated periodontitis have been recognized in ESRD limiting the magnitude of the effect²¹. Therefore, untreated periodontitis may be a forgotten comorbidity. This proposal aims to assess the anti-inflammatory effect of repeated and regular oral health interventions, which will target periodontitis in ESRD. **We hypothesize** that there is a difference in the response to repeated and ongoing vs. single periodontal interventions as measured by: a) patient-centered outcomes, b) inflammatory, oxidative stress and nutritional biomarkers as well as c) clinical oral outcomes. This will be achieved by following specific aims:

Specific aim 1: We aim to compare the difference (Δ) in patient-centered as well as clinical oral outcomes between ESRD subjects receiving repeated (Test group) and the standard-of-care (Control) periodontal therapy. For this aim, we will measure and compare patient-centered outcome (Oral Health Impact Profile-14 survey) reflecting patient's perspective on oral health at baseline and 6-months. The clinical oral outcomes will evaluate the clinical response and effectiveness of the intervention at each time point.

Specific aim 2: We aim to compare the difference (Δ) in outcomes of systemic inflammation (*Creactive protein, Interleukin 6*), oxidative stress (F2-isoprostanes, and isofurans), and nutrition (albumin) in the repeated vs. standard-of-care periodontal therapy in ESRD at baseline and 6-months. To accomplish this, we will collect blood samples from all patients at each time point. Serial changes of the inflammatory and oxidative stress markers will also be evaluated during the observational period and correlated with clinical disease markers.

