1) Inflammatory Markers (Primary Outcomes) and Oxidative Stress Markers (Secondary outcomes): We aim to measure serum CRP (primary outcome) as a biomarker of inflammation as well as IL-6, F2 isofurans and F2 isoprostanes as markers of oxidative stress linked to atherosclerosis and poor CVD in ESRD²². A single serum CRP elevated measure has been shown to predict poor outcomes and sudden death in ESRD⁷⁵. Additional studies showed that IL-6 has been determined as a direct promoter of atherosclerosis and protein energy wasting through mechanisms of vascular calcification, muscle catabolism and cell aging ³² predicting poor outcomes in ESRD⁷⁵. In addition to testing the primary and secondary outcomes at baseline and 6-month, we will compare serial changes of the biomarkers throughout the study period at 2- and 4-month time points. Moreover, we will also measure F2 isoprostanes and isofurans, which are chemically stable, precise and easily detectable markers of lipid peroxidation⁷⁶ associated with poor outcomes in ESRD.²⁰

- *2) Patient-centered outcome (Secondary outcome):* Given the wide recognition of patient-centered outcome research by the Agency for Healthcare Research and Quality (AHRQ) and the NIH ⁷⁷, the validated OHIP-14 (true outcome) will evaluate patient's perception of oral status change ⁷⁸ and predictably assess periodontal treatment effect on oral health quality of life ^{79, 80}. Oral health perception has been determined fair to poor in groups of ESRD patients ⁸¹. The oral health related quality of life will be assessed with the OHIP-14 questionnaire ⁸². The response codes for the items in this tool are based on a five-point scale, ranging from "never" to "all the time".
- 3) Clinical Periodontal Parameters (Secondary Outcomes): The baseline full mouth periodontal examination will include missing teeth, probing depth (PD), bleeding on probing (BOP), clinical attachment loss (CAL), and plaque score (PS) at six sites on all teeth. BOP is an indicator of gingival (gum) inflammation and presence of active disease 83 . Periodontal parameters will be measured at baseline, at 2-, 4- and 6-months. Changes in probing depth (Δ PD) and BOP (Δ BOP) will be considered as the clinical outcome of treatment effectiveness and clinical response.

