Visit 5; Test (1-month post-Day 0): Oral hygiene reinforcement and behavioral modification only for the Test arm.

Visit 6; Test (2-month post-Day 0): Full mouth periodontal examination including oral hygiene assessment will be performed. Both arms will receive the OHIP-14. Blood samples (6.5ml) will be collected for inflammatory, oxidative stress and nutritional markers for both arms. Only in the test arm, the subject will receive supportive periodontal treatment including supragingival debridement and mechanical instrumentation (tooth cleaning) and oral hygiene reinforcement. Any remaining pockets will be treated with limited deep cleaning with local anesthesia. The control arm will receive no intervention. Visit 7; Test (3-month post-Day 0): Oral hygiene reinforcement and behavioral modification only for the Test arm.

Visit 8; Test (4-month interval post-Day o): Full mouth periodontal examination including oral hygiene assessment will be performed. Both arms will receive the OHIP-14. Blood samples (6.5ml) will be collected for inflammatory, oxidative stress and nutritional markers for both arms. Only in the test arm, the subject will receive supportive periodontal treatment including supragingival debridement and mechanical instrumentation (tooth cleaning) and oral hygiene reinforcement. Any remaining pockets will be treated with limited deep cleaning with local anesthesia. The control arm will receive no intervention. Visit 9; Test (5-month post-Day o): Oral hygiene reinforcement and behavioral modification only for the Test arm.

Visit 10; Test (6-month post-Day 0): Full mouth periodontal examination including oral hygiene assessment will be performed. Both arms will receive the OHIP-14. Blood samples (6.5ml) will be collected for inflammatory, oxidative stress and nutritional markers for both arms. At the end of the study both arms will receive supportive periodontal treatment including supragingival debridement and mechanical instrumentation (tooth cleaning) and oral hygiene reinforcement. Any remaining pockets will be treated with limited deep cleaning with local anesthesia.

Control arm: (see time table control arm, pg. 15)

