Recruitment and Consent Procedures: Patient recruitment was initiated on November 7th, 2017 with expected enrollment completion in April 2019. The trial is currently recruiting patients at UCONN Dialysis/DCI and DCI Manchester. The recruitment strategy includes study fliers posted in different locations including UCONN Health Nephrology, Dental Clinics and Dialysis Outpatient Units. All recruitment strategies and material were approved by UCONN Institutional Review Board (IRB) and DCI ARO. Figure 2 represents study flow chart.

The initial patient selection is based upon administrative and medical record review by the nurse manager with the utilization of the study's pre-screening form. The nephrologist reviews the patient selection and, based on clinical judgment and the pre-screening criteria makes the recommendation. We have also developed recruitment tools (pre-screening forms, study brochures), which are practical and easy to implement in order to assist the nephrologist and dialysis personnel during the pre-screening process. Once the pre-screening process is completed and the patient agrees to be approached, the study coordinator meets with the ESRD patient to present the study, the overall risk/benefits analysis, written consent is sought from each of the participants. The consent process may be extended to more than one meeting given the patient's level of fatigue [37].

Randomization and Allocation: The study follows a block randomization scheme. Blocks will be determined as per 2X2X2 a priori categorization of age, race and gender. More specifically, the participants in two dialysis units (UCONN Dialysis/DCI and DCI Manchester) will be randomly assigned to the study arms using a computer randomization program supervised by the study's biostatistician. Once sequences are determined, they remained concealed in opaque envelopes and opened prior to enrollment in the unit by the study coordinator.

Examiner calibration: The calibrated dental hygienist practices under the supervision of the Principle Investigator (PI). Following the calibration process, there was an agreement within ± 1 mm of 96%. Blinding: At 6-month visit, the final assessment will be conducted by the PI, who will be blinded to the study arm.

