The PI and the study coordinator are in charge for reporting the adverse events and also the follow up visit with the subject. Further, any protocol deviation is documented and reported. All laboratory assessments are maintained in a log list with specimen numbers and dates. An important part of the study is the quality management plan, which ensures study quality and adherence to the protocol standards. To achieve this, we have established an extensive monitoring plan to secure the study design, and achieve the endpoints and outcomes. Weekly study team communication and meetings are scheduled to prevent any misunderstandings or protocol gaps. The meetings help the team resolve problems and move to corrective actions at once before they become an established pattern. Every three months, the study subject charts are audited internally. To ensure the presence of consent form, pre-screen and screening form, lab requests, data collection forms, missed appointments and notes. Further, the electronic data files and all data variables are crosschecked with the source original data. The subject ID will be also crosschecked. Missing data will be left blank. Merging files of laboratory and clinical variables will be performed carefully based on ID variable.

Study Rigor and Transparency: The proposed trial follows a rigorous and transparent study design as requiring by the NIH capturing elements of trail design, pre-specified eligibility criteria, pre-specified primary and secondary outcomes, detailed intervention description to allow replication, intervention random allocation and concealment, blinding in outcome assessment, appropriate sample size calculations, explanation of interim analysis, as per CONSORT Guidelines[45, 46]. The proposed methods secures a robust and unbiased analysis as expected in a randomized controlled trial (RCT) and will ensure reproducibility of the experimental design[47]. With these efforts, we acknowledge the importance of research transparency through updated trial status, result and data reporting on Clinicaltrials.gov, as expected[48].

Timetable: Test Arm

Intervention	Visit 1	Visit 2 Baseline	Visit 3-4 Day 0	Visit 5 1-month	Visit 6 2-month	Visit 7 3-month	Visit 8 4-month	Visit 9 5-month	Visit 10 6-month
Consent Form	x								
Medical History	x								
Review/Vitals									
Periodontal	x								
Screening									
Full mouth		x			x		x		x
periodontal exam									
OHIP-14		x			x		x		x
Periodontal			x						
Therapy (Deep									

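### Only the 6-month periodontal examination is stated to be masked, yet Aim 1 also judges effectiveness from the 2- and 4-month pocket-depth and bleeding readings

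*Protocol*

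**What the plan says.** - **Masking.** The Blinding paragraph, directly after Examiner calibration, states: "At 6-month visit, the final assessment will be conducted by the PI, who will be blinded to the study arm". No other text gives the masking status of a particular examination.
- **Examiners.** Examiner calibration names a calibrated dental hygienist who works under the PI's supervision and reports: "Following the calibration process, there was an agreement within ± 1 mm of 96" per cent. Screening at Visit 1 may be done by a dentist or a hygienist. Nobody is named for the baseline, 2-month or 4-month full-mouth examination.
- **Outcome.** Under Outcomes and Rationale, item 3: "Periodontal parameters will be measured at baseline, at 2-, 4- and 6-months". Change in PD and BOP is the clinical measure of effectiveness and response, and is secondary. Specific aim 1 uses the clinical outcomes to evaluate "clinical response and effectiveness of the intervention at each time point".
- **Treatment at the examination visits.** For the 2- and 4-month visits, after the examination: "Only in the test arm, the subject will receive supportive periodontal treatment", including limited deep cleaning of pockets that remain. The control arm gets no intervention. At 6 months both arms are treated.
- **General claim.** Study Rigor and Transparency lists "blinding in outcome assessment" among the design features, without restricting it to a visit.
- **Monitoring.** The Data and Safety Monitoring Plan names the PI among the safety monitors and lists un-blinded data among the data reviewed.

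**The concern.** PD and BOP depend on probing force, angulation and judgement at the margin, so an examiner who knows the arm can shift them without intending to. At 2 and 4 months the circumstances make knowledge of the arm easy: one arm is treated straight after the examination and the other is not, and the readings show which pockets remain to be cleaned. If those readings are then used as evidence that repeated therapy works, part of an apparent benefit could be expectation. A reader who relies on the general blinding statement would not see this limit. The trial is also meant to supply effect estimates for a larger trial, so an inflated interim clinical effect could be carried forward.

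**Working it through.** **1. Masking, visit by visit**

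| Examination | Used as clinical outcome (Aim 1, Outcomes item 3) | Examiner named | Masking stated | Treatment at that visit |
|---|---|---|---|---|
| Baseline | reference value for change | no | no | none |
| 2 months | yes | no | no | test arm only |
| 4 months | yes | no | no | test arm only |
| 6 months | yes | PI | yes | both arms |

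Three post-treatment readings enter the outcome. One is stated to be masked, so 3 − 1 = 2 of 3 are not. The 6-month visit also treats both arms alike, so that visit's procedures do not reveal the arm. Earlier visits do: besides the arm-specific treatment, the test arm alone attends at 1, 3 and 5 months, and after Day 0 the visit numbers differ by arm (the 2-month visit is Visit 6 for test and Visit 5 for control).

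**2. Scale of possible assessor bias (illustrative)**

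The protocol gives no figure for assessor bias. Assumptions: no true difference; bias of *b* SD between arms; 28 analysable per arm; normal test, two-sided 5%. The 28 comes from Power Analysis, where it was calculated for CRP. With d = 0.67 and 80% power it reproduces at a one-sided 5% level (28); a two-sided level gives 35. It serves here only as the number analysed.

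SE of the difference in SD units = √(2/28) = 0.267. Rejection probability = 1 − Φ(1.96 − b/0.267) + Φ(−1.96 − b/0.267).

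| b (SD) | b/0.267 | Rejection probability |
|---|---|---|
| 0 | 0 | 5.0% |
| 0.1 | 0.37 | 6.6% |
| 0.2 | 0.75 | 11.6% |
| 0.3 | 1.12 | 20.2% |
| 0.5 | 1.87 | 46.5% |

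**3. Would a change of examiner at 6 months bias the arm comparison?**

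Suppose the 6-month examiner reads *s* mm deeper than the baseline examiner in both arms.

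- Test-arm change: (T6 + s) − T0
- Control-arm change: (C6 + s) − C0
- Difference between arms: (T6 − T0) − (C6 − C0)

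The shift *s* cancels between arms. It stays in each arm's own change, and in any description across the four visits.

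**4. The general claim against the specific one**

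Study Rigor and Transparency claims masked outcome assessment without limit, whereas the Blinding paragraph provides it for one visit. The specific text governs conduct, so the general text says more than the design delivers.

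**5. How secure the 6-month masking is**

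The PI makes the masked reading and is also a safety monitor in a plan whose data include un-blinded data. The plan does not say which monitor sees which data. This does not show that the PI is unmasked, but nothing in the text prevents it.

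**The case against.** **The examiner at 2 and 4 months may be masked in practice.** The examination is listed before the treatment, and a separate person could treat from the chart. A reader might infer that an unmasked hygienist does all the earlier examinations, because the hygienist is named under Examiner calibration and the PI is then assigned the final visit. That is the likely reading, but no text assigns those visits to the hygienist or calls the hygienist unmasked. What stands is narrower: the examiner is not named and masking is not stated.

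**Two examiners.** A reader might also infer that a change of examiner spoils the baseline-to-6-month comparison. The documents do not establish that the examiners differ. Even if they do, a shift common to both arms cancels from the between-arm difference that the aims address. The calibration figure does not settle the matter either way: it does not say whether agreement is between or within examiners, does not cover bleeding, and cannot speak to bias from knowing the arm.

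**No interim test is planned.** Statistical methods names change in CRP and IL-6 as the dependent variables for testing between arms, and offers descriptive analysis at all four time points. No between-arm test of PD or BOP at 2 or 4 months is specified, and ranking time points could be left to an analysis plan that is not shown. This limits the harm. It does not remove it, because Aim 1 itself bases effectiveness on each time point, and masking is trial conduct that the protocol fixes.

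**The general blinding phrase is one item in a list.** That is fair: it is an overstatement that the specific paragraph corrects, not a contradiction that would misdirect staff.

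**Conclusion.** The point holds in a limited form. Two of the three post-treatment PD and BOP assessments have no stated masking, although Aim 1 uses them to judge effectiveness, and the general blinding claim is too broad. Between-arm clinical results at 2 and 4 months are open to assessor bias. Its size is unknown; the 6.6% to 46.5% range rests on an assumed bias of 0.1 to 0.5 SD, 28 per arm and a two-sided 5% test.

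The 6-month between-arm comparison is sound on the stated design, provided that the PI stays masked and the baseline readings do not depend on arm. Both arms follow the same listed procedures through the Day 0 treatment, which supports the second condition. If the baseline and 6-month examiners differ, only within-arm change and descriptions across visits are distorted.

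PD and BOP are secondary outcomes. CRP, the primary outcome, is measured by ELISA on coded samples (Blood Collection and Analyses) and is not affected. The text should be changed, but the trial's main question does not depend on it.

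**What to change.** 1. In Specific aim 1 and Outcomes and Rationale, make the masked 6-month between-arm comparison of PD and BOP, adjusted for the baseline value, the clinical outcome of Aim 1.
2. Report the 2- and 4-month clinical results, and within-arm change to 6 months, as descriptive and not masked.
3. Under Study Rigor and Transparency, limit the blinding claim to the 6-month examination.
4. In the Data and Safety Monitoring Plan, state that the PI sees no arm-level or un-blinded monitoring data before completing the 6-month examinations.

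The cost is wording and some separation of duties in monitoring, with no new visits or procedures. The downside is that interim clinical results carry less weight. Moving the PI to the baseline examination is not advised now: recruitment began in November 2017, so the change would mix baseline examiners by enrolment date, and the between-arm comparison does not need it.
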